## 7.2 CV Event Endpoint Definitions

CV death, stroke, TIA, non-elective coronary revascularization, hospitalization for unstable angina, and hospitalization for HF will be defined based on the 2017 Cardiovascular and Stroke Endpoint Definitions for Clinical Trials described in Appendix F. MI will be defined based on the Fourth Universal Definition of Myocardial Infarction described in Appendix G.

An independent CEC will adjudicate all events of death and all potential or suspected CV events. Additional details will be provided in the CEC Charter.

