## 7.2.4 Non-Elective Coronary Revascularization

Coronary revascularization includes any coronary arterial vascular intervention done to treat clinical or functional ischemia and/or prevent major ischemic events, including PCI or surgical intervention of the coronary arteries.

A non-elective coronary revascularization includes "emergent" or "urgent" classification, as defined by the following:

• Emergency: The procedure should be performed as soon as possible because of substantial concerns that ongoing myocardial ischemia and/or MI could lead to death. "As soon as possible" refers to a participant who is of sufficient acuity that one would cancel a scheduled case to perform this procedure immediately in the next available room during business hours, or one would activate the on-call team were this to occur during off-hours; and

• Urgent: The procedure should be performed on an inpatient basis and prior to discharge because of significant concerns that there is risk of myocardial ischemia, MI, and/or death. Participants who are outpatients or in the emergency department at the time that the cardiac catheterization is requested would warrant hospital admission based on their clinical presentation.

More details regarding the classification of coronary revascularization procedures are provided in Appendix F.

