#### 8.3 Serious Adverse Events

An AE or adverse reaction is considered serious if, in the view of either the Investigator or Sponsor, it results in any of the following outcomes:

- Death;
- A life-threatening AE;

Note: An AE or adverse reaction is considered "life-threatening" if, in view of either the Investigator or Sponsor, its occurrence places the participant at immediate risk of death. It does not include an event that, had it occurred in a more severe form, might have caused death.

• Requires hospitalization or prolongation of existing hospitalizations;

Note: Any hospital admission with at least 1 overnight stay will be considered an inpatient hospitalization. An emergency room or urgent care visit without hospital admission will not be recorded as an SAE under this criterion, nor will hospitalization for a procedure scheduled or planned before signing of informed consent, or elective treatment of a pre-existing condition that did not worsen from Baseline. However, unexpected complications and/or prolongation of hospitalization that occur during elective surgery should be recorded as AEs and assessed for seriousness. Admission to the hospital for social or situational reasons (ie, no place to stay, live too far away to come for hospital visits, respite care) will not be considered inpatient hospitalizations.

- A persistent or significant disability/incapacity or substantial disruption of the ability to conduct normal life functions:
- A congenital anomaly/birth defect; or
- An important medical event.

Note: Important medical events that do not meet any of the above criteria may be considered an SAE when, based upon appropriate medical judgment, they may jeopardize the participant and may require medical or surgical intervention to prevent 1 of the outcomes listed above. Examples of such medical events include allergic bronchospasm requiring intensive treatment in an emergency room or at home, blood dyscrasias or convulsions that do not result in inpatient hospitalizations, or the development of drug dependency.

SAEs that meet the definition of CV outcome events should also be captured in the CV events eCRF.

The plan for exemption from expedited SAE reporting for disease-related events will be described in the Statistical Analysis Plan (SAP), Data Management Plan, and CEC Charter documents.

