- 11. It should be ensured that a repeat assessment (if necessary) is completed within the respective visit window and that the assessment is not done concurrently with other study procedures.
- 12. A single 12-lead ECG will be performed in the supine position after 10 minutes of rest.
- 13. Participants must fast for a minimum of 8 hours prior to samples being collected.
- 14. Samples should be collected prior to study drug administration.
- 15. Serum archive sample is not collected in China.
- 16. Only hsCRP will be assessed at Screening (Visit 1).
- 17. Urine dipstick analysis will be performed locally from a sample of mid-stream urine. In case of abnormal results, microscopy and other assessments will be performed at the local laboratory and the abnormality recorded as an AE.
- 18. A PK sample will be collected prior to study drug administration for trough measurement of obicetrapib in plasma. At Visits 2, 5, and 7, participants should take study drug after a trough PK sample has been drawn.
- 19. CV events include CV death, non-fatal myocardial infarction, non-fatal stroke, non-elective coronary revascularization, hospitalization for unstable angina and/or chest pain, hospitalization for heart failure, and transient ischemic attack.

ABPM = ambulatory blood pressure monitoring; AE = adverse event; ApoA1 = apolipoprotein A1; BMI = body mass index; CV = cardiovascular; ECG = electrocardiogram; EOS = End of Study; EOT = End of Treatment; ET = Early Termination; FSH = follicle-stimulating hormone; HOMA-IR = homeostatic model assessment of insulin resistance;

hsCRP = high sensitivity C-reactive protein; ICF = informed consent form; Lp(a) = lipoprotein (a); PK = pharmacokinetic(s); TSH = thyroid-stimulating hormone; UACR = urine albumin-creatinine ratio; UPCR = urine protein-creatinine ratio; V = Visit.

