18. A PK sample will be collected prior to study drug administration for trough measurement of obicetrapib in plasma. At Visits 2, 5, and 7, participants should take study drug after a trough PK sample has been drawn.
19. CV events include CV death, non-fatal myocardial infarction, non-fatal stroke, non-elective coronary revascularization, hospitalization for unstable angina and/or chest pain, hospitalization for heart failure, and transient ischemic attack.
20. The PK sample at Visit 4 is not designated in the protocol, however the PK will be assessed using residual serum from the Day 84 limited chemistry panel to confirm participants are taking study drug.

ABPM = ambulatory blood pressure monitoring; AE = adverse event; ApoA1 = apolipoprotein A1; BMI = body mass index; CV = cardiovascular; ECG = electrocardiogram; EOS = End of Study; EOT = End of Treatment; ET = Early Termination; FSH = follicle-stimulating hormone; HOMA-IR = homeostatic model

assessment of insulin resistance; hsCRP = high sensitivity C-reactive protein; ICF = informed consent form; Lp(a) = lipoprotein (a); PK = pharmacokinetic(s); TSH = thyroid-stimulating hormone; UACR = urine albumin-creatinine ratio; UPCR = urine protein-creatinine ratio; V = Visit.

2.2.2 *Sample Size Determination*

Enrollment of approximately 2400 participants globally is planned for this study.

Assuming an approximate 5% drop out rate, approximately 2280 participants will be evaluable for efficacy. This sample size of at least 2280 evaluable participants will provide more than 90% power to detect a 30% reduction of LDL-C (standard deviation 15%) levels in the obicetrapib group compared to the placebo group at a 1-sided significance level of 0.025. This sample size will also contribute to sufficient participant exposure and safety data.

ABPM substudy

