- The time from Randomization until the first confirmed occurrence of a composite of CV death, non-fatal MI, or non-fatal stroke, or coronary revascularization;
- The time from Randomization until the first confirmed occurrence of a composite of CV death, non-fatal MI, or non-fatal stroke; and
- The time from Randomization until the first confirmed occurrence of hospitalization for unstable angina and/or chest pain, hospitalization for HF, and TIA;
- The time from Randomization until the first confirmed occurrence of MALE event. The MALE event will include acute limb ischemia, major amputation, urgent revascularization.
- The time from Randomization until the first confirmed occurrence of a composite of CHD death, non-fatal MI, or non-fatal stroke, or non-elective coronary revascularization;

- The time from Randomization until the first confirmed occurrence of a composite of CHD death, non-fatal MI, or non-fatal stroke, or coronary revascularization;
- The time from Randomization until the first confirmed occurrence of a composite of CHD death, non-fatal MI, or non-fatal stroke;
- The time from Randomization until the first confirmed occurrence of a composite of CV death, non-fatal MI, non-fatal stroke, hospitalization of unstable angina, or non-elective coronary revascularization;
- The time from Randomization until the first confirmed occurrence of a composite of CV death, non-fatal MI, non-fatal stroke, hospitalization of unstable angina, or coronary revascularization;
- The time from Randomization until the first confirmed occurrence of a composite of CHD death, non-fatal MI, non-fatal stroke, hospitalization of unstable angina, or non-elective coronary revascularization;
- The time from Randomization until the first confirmed occurrence of a composite of CHD death, non-fatal MI, non-fatal stroke, hospitalization of unstable angina, or coronary revascularization;
- The time from Randomization until the first confirmed occurrence of a composite of CV death, non-fatal MI, non-fatal stroke, hospitalization of unstable angina, MALE, or non-elective coronary revascularization;
- The time from Randomization until the first confirmed occurrence of a composite of CV death, non-fatal MI, non-fatal stroke, hospitalization of unstable angina, MALE, or coronary revascularization;

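### SAP 2.3.3 counts elective coronary revascularization or limb events in 25 of 46 exploratory cardiovascular endpoints, but the CV-event list was not widened to collect them

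*SAP*

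**What the plan says.** **Endpoints.** SAP 2.3.3 extends the protocol's three cardiovascular time-to-event endpoints to a long list. One addition is the time to first confirmed occurrence of "a composite of CV death, non-fatal MI, or non-fatal stroke, or coronary revascularization"; it stands beside a composite that differs only in requiring the revascularization to be non-elective. Another is a limb endpoint: "The MALE event will include acute limb ischemia, major amputation, urgent revascularization". Both components recur through the larger composites and the total-event counts.

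**Collection.** Footnote 19 to the schedule in Protocol Appendix A sets out what is assessed at each visit: "CV events include CV death, non-fatal myocardial infarction, non-fatal stroke, non-elective coronary revascularization, hospitalization for unstable angina and/or chest pain", then hospitalization for heart failure and TIA. Footnote 19 to SAP Table 1 repeats this list unchanged.

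**Definitions.** Protocol 7.2 says "CV death, stroke, TIA, non-elective coronary revascularization, hospitalization for unstable angina, and hospitalization for HF will be defined" from the published 2017 endpoint definitions, with MI defined separately. Protocol 7.2.4 also has a general definition: "Coronary revascularization includes any coronary arterial vascular intervention done to treat clinical or functional ischemia and/or prevent major ischemic events". Appendix F defines an elective PCI status and, for peripheral procedures, emergent and urgent status.

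**AE and SAE rules.** Under Protocol 8.2 the condition leading to a procedure is the AE and the procedure is not; a condition present at Screening is an AE only if it changes. Under Protocol 8.3, hospitalization for a procedure planned before consent, "or elective treatment of a pre-existing condition that did not worsen from Baseline", is not an SAE under the hospitalization criterion.

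**Identification.** SAP 3.4.3 identifies AAA and carotid revascularization by the preferred terms in SAP Appendix C. Where no adjudicated date applies, it uses the eCRF date.

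**The concern.** The SAP can count only what the protocol has sites record. It widened the endpoints but not the list of events that sites are asked about. It did annotate the same table where another data source departs from the protocol: footnote 20 explains the added Visit 4 PK sample. Footnote 19 received no such note.

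Hazard ratios and rate ratios will be produced for these composites. A reader who sees the any-revascularization and non-elective results agree could conclude that elective procedures were rare. A reader who sees few limb events could conclude that limb events were rare. Either pattern could instead reflect what was collected.

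**Working it through.** Neither document states a number of cardiovascular endpoints, an event rate or a power for them, so there is no planned figure to reproduce. The check is a count of SAP 2.3.3 followed by a comparison of collection routes.

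**1. Count of bullets in SAP 2.3.3** (all-cause death included)

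| | Time to event | Total events | Sum |
|---|---|---|---|
| All cardiovascular bullets | 27 | 19 | 46 |
| Any coronary revascularization | 8 | 8 | 16 |
| MALE | 9 | 8 | 17 |
| Both | 4 | 4 | 8 |
| Either | 8 + 9 − 4 = 13 | 8 + 8 − 4 = 12 | 25 |

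Check: 16 + 17 − 8 = 25, and 25/46 = 54%. The three-component CV-death and CHD-death composites each appear twice as time-to-event bullets, so 46 − 2 = 44 are distinct. Neither duplicate is among the 25, and 25/44 = 57%. The composition of the last bullet, the number of total CV events, is not stated; if it includes these events the count is 26.

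**2. Twins.** Each of the 16 any-revascularization endpoints was matched to an otherwise identical non-elective endpoint; all 16 have one. Let E be the number of recorded elective procedures that count towards an endpoint.

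- Total events: N(any) = N(non-elective) + E.
- Time to first: T(any) = min[T(non-elective composite), T(first recorded elective procedure)].

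If E = 0, both reduce to the twin for every participant, and the hazard or rate ratio is the same number. The share of elective procedures lost can lie anywhere from none to all. The documents give neither an event rate nor an elective share, so it cannot be narrowed.

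**3. Routes into the data**

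| Route | Elective coronary revascularization | Acute limb ischemia, major amputation |
|---|---|---|
| Footnote 19, both documents | Not listed | Not listed |
| Protocol 7.2 list | Non-elective only | Not listed |
| Criteria elsewhere | Protocol 7.2.4 in general; elective PCI status in Appendix F | None; acute limb ischemia is only an example under emergent peripheral procedures |
| AE (Protocol 8.2) | Condition only, and only if changed since Screening | Condition recorded |
| SAE by hospitalization (Protocol 8.3) | Not for elective treatment of an unworsened condition | Usually yes |
| Procedure record (Protocol 5.6.3) | Medications only are required | Medications only are required |
| SAP term list | None | None (AAA and carotid have Appendix C) |

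Take a participant with coronary disease at Screening who has an elective PCI without worsening. The event is not on the CV-event list, does not generate an AE, and is not an SAE under the hospitalization criterion. The eCRF-date rule in SAP 3.4.3 helps only if a record exists. For limb events an SAE is likely, but Protocol 8.3 sends an SAE to the CV-events eCRF only when it meets a CV outcome definition, and no such definition is given for these two.

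**The case against.** **The stronger reading.** A reader might infer that these endpoints will be under-counted, or cannot be measured at all. The documents do not show that. The committee is to adjudicate all potential or suspected CV events, footnote 19 uses a verb that need not be exhaustive, and neither the eCRF nor the committee charter is available. Absence from a footnote does not prove absence from collection. This stands, and it limits the conclusion to a risk of incomplete capture. It does not remove the gap: footnote 19 is the only statement of which events count as CV events at a visit, and nothing in the text requires an elective procedure to be recorded.

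**Definitions.** It would also be wrong to say that these events lie wholly outside the adjudication definitions. Coronary revascularization in general, elective PCI status and urgent peripheral intervention are all defined. Only acute limb ischemia and major amputation lack criteria.

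**Urgent PCI as MALE.** The MALE wording names no vascular bed, so a literal reader might count an urgent PCI. The name itself restricts the event to the limb, and 16 of the 17 MALE endpoints already include coronary revascularization. The literal reading matters mainly for the one stand-alone MALE endpoint; it warrants a wording correction and no more.

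**Consequence.** All these endpoints are exploratory, without multiplicity adjustment, and SAP section 6 declares MALE and any coronary revascularization as additions. Treatment and lipid values are blinded, so incomplete capture should affect both arms similarly and cost events rather than create an effect. This stands. What remains is that a composite may not contain the events its name promises.

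**Conclusion.** The point holds as a conflict between the SAP's endpoint list and the trial's stated collection rules. It touches 25 of 46 bullets (44 distinct), but these are two component questions repeated through overlapping composites rather than 25 separate faults.

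Elective coronary revascularization is the main exposure: 16 endpoints claim to count it, and no rule requires it to be recorded. MALE is the lesser one: most events should surface as SAEs, but two of its three components have no criteria or term list, so identification may vary.

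The conclusion assumes that the unseen eCRF and charter follow footnote 19 and Protocol 7.2. If they are wider, the remaining fault is that the SAP does not state the data source. The equality with the twins requires that no elective procedure is recorded and treats the salvage PCI status in Appendix F as non-elective. The size of any loss cannot be computed. Primary and secondary conclusions are unaffected.

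**What to change.** 1. Align footnote 19, the CV-event eCRF and the adjudication scope with SAP 2.3.3. Add elective coronary revascularization, using Protocol 7.2.4 and the Appendix F status categories, and state that these apply to CABG, since Appendix F gives them for PCI. Add the limb events, with criteria for acute limb ischemia and major amputation.
2. Where these events were not prospectively collected, label the affected endpoints AE-derived, unadjudicated and incomplete, and do not present the any-revascularization composites as distinct from their non-elective twins.
3. In either case, add a MALE preferred-term list beside SAP Appendix C, and change the MALE component to urgent peripheral (limb) revascularization. The list should include conditions as well as procedures, because Protocol 8.2 records the condition. The two duplicate bullets can be removed in the same edit.

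For events still to be collected, item 1 is a small collection and charter update. Retrospective collection would reach about 2400 participants at about 180 sites, which is why item 2 is offered. Items 2 and 3 are SAP wording and programming; their price is a less favourable label on exploratory tables.

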#### 7.2.1 CV Death

CV death is defined as death resulting from an acute MI, sudden cardiac death, death due to HF, death due to stroke, death due to CV procedures, death due to CV hemorrhage, or death due to other CV causes.

Death due to acute MI refers to death by any CV mechanism (eg, arrhythmia, sudden death, HF, stroke, pulmonary embolus, peripheral arterial disease) ≤30 days after an MI, related to the immediate consequences of the MI (eg, progressive HF or recalcitrant arrhythmia). Death resulting from a procedure to treat an MI (eg, PCI, CABG surgery), or to treat a complication resulting from an MI, should also be considered a death due to an acute MI.

Sudden cardiac death refers to death that occurs unexpectedly and not within 30 days of an acute MI. Death due to HF refers to death in association with clinically worsening symptoms and/or signs of HF regardless of HF etiology. Death due to stroke refers to death after a stroke that is

either a direct consequence of the stroke or a complication of the stroke. Death due to CV procedures refers to death caused by the immediate complications of a cardiac procedure. Death resulting from an elective coronary procedure to treat myocardial ischemia or death due to an MI that occurs as a direct consequence of a CV investigation, procedure, or operation should be considered as a death due to CV procedure. Death due to CV hemorrhage refers to death related to hemorrhage such as a non-stroke intracranial hemorrhage (eg, subdural hematoma), non-procedural or non-traumatic vascular rupture (eg, aortic aneurysm), or hemorrhage causing cardiac tamponade.

Death due to other CV causes refers to CV death not included in the above categories but with a specific, known cause (eg, pulmonary embolism or peripheral arterial disease).

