2 STUDY OVERVIEW

2.1 Study Objectives

2.1.1 *Primary Objective*

The primary objective of this study is to evaluate the effect of obicetrapib on low-density lipoprotein cholesterol (LDL-C) levels at Day 84.

2.1.2 *Secondary Objective*

The secondary objectives of this study include the following:

- To evaluate the effect of obicetrapib on LDL-C levels at Days 180 and 365;
- To evaluate the effect of obicetrapib on apolipoprotein B (ApoB), non-high-density lipoprotein cholesterol (non-HDL-C), high-density lipoprotein cholesterol (HDL-C), total cholesterol (TC), and triglycerides (TG) at Days 84, 180, and 365;
- To evaluate the effect of obicetrapib on lipoprotein (a) (Lp[a]) and apolipoprotein A1 (ApoA1) at Day 84; and
- To evaluate the safety and tolerability profile of obicetrapib in a representative population of adult males and females with heterozygous familial hypercholesterolemia (HeFH) and/or ASCVD of all ages, assessed by adverse events (AEs), events of special interest (ESIs), vital signs (including blood pressure), electrocardiogram (ECG) measurements, and clinical laboratory values.

2.1.3 *Exploratory Objectives*

The exploratory objectives of this study include the following:

- To evaluate the effect of obicetrapib on the following:
 - Proportion of participants achieving prespecified LDL-C levels at Days 84, 180, and 365; and
 - Biomarkers, including glycosylated hemoglobin (HbA1c), homeostatic model assessment of insulin resistance (HOMA-IR), and blood glucose at Day 365.
- To evaluate trough levels of obicetrapib from Baseline to Day 84, 180 and 365 in the obicetrapib group;
- To evaluate the effect of obicetrapib on cardiovascular events
 - CV death, non-fatal myocardial infarction (MI), non-fatal stroke, or non-elective coronary revascularization; and

- CV death, non-fatal myocardial infarction (MI), non-fatal stroke, or coronary revascularization; and
- CV death, non-fatal myocardial infarction (MI), non-fatal stroke
- Major Adverse Limb Events (MALE) events
- Coronary heart disease (CHD) death, non-fatal myocardial infarction (MI), non-fatal stroke, or non-elective coronary revascularization; and
- CHD death, non-fatal myocardial infarction (MI), non-fatal stroke, or coronary revascularization; and
- CHD death, non-fatal myocardial infarction (MI), non-fatal stroke
- Total CV events

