- The time from Randomization until the first confirmed occurrence of a composite of CHD death, non-fatal MI, non-fatal stroke, hospitalization of unstable angina, MALE, or non-elective coronary revascularization;
- The time from Randomization until the first confirmed occurrence of a composite of CHD death, non-fatal MI, non-fatal stroke, hospitalization of unstable angina, MALE, or coronary revascularization;
- The time from Randomization until the first confirmed occurrence of a composite of CV death, non-fatal MI, non-fatal stroke, hospitalization of unstable angina, MALE, other atherosclerotic events (AAA, TIA, carotid revascularization), or non-elective coronary revascularization;
- The time from Randomization until the first confirmed occurrence of a composite of CV death, non-fatal MI, non-fatal stroke, hospitalization of unstable angina, MALE, other atherosclerotic events (AAA, TIA, carotid revascularization), or coronary revascularization;
- The time from Randomization until the first confirmed occurrence of a composite of CHD death, non-fatal MI, non-fatal stroke, hospitalization of unstable angina, MALE, other atherosclerotic events (AAA, TIA, carotid revascularization), or non-elective coronary revascularization;

- The time from Randomization until the first confirmed occurrence of a composite of CHD death, non-fatal MI, non-fatal stroke, hospitalization of unstable angina, MALE, other atherosclerotic events (AAA, TIA, carotid revascularization), or coronary revascularization;
- The time from Randomization until the first confirmed occurrence of a composite of CV death, non-fatal MI, or non-fatal stroke;
- The time from Randomization until the first confirmed occurrence of a composite of CHD death, non-fatal MI, or non-fatal stroke;
- The time from Randomization until the confirmed occurrence of CV death;
- The time from Randomization until the confirmed occurrence of non-fatal MI;
- The time from Randomization until the confirmed occurrence of non-fatal stroke;
- The time from Randomization until the confirmed occurrence of non-elective coronary revascularization ;
- The time from Randomization until the confirmed occurrence of all cause death;
- The number of total events: CV death, non-fatal MI, non-fatal stroke;
- The number of total events: CHD death, non-fatal MI, non-fatal stroke;
- The number of total events: CV death, non-fatal MI, non-fatal stroke, or non-elective coronary revascularization;

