- The number of total events: CV death, non-fatal MI, non-fatal stroke, or all coronary revascularization;
- The number of total events: CHD death, non-fatal MI, non-fatal stroke, or non-elective coronary revascularization;
- The number of total events: CHD death, non-fatal MI, non-fatal stroke, or all coronary revascularization;
- The number of total events: CV death, non-fatal MI, non-fatal stroke, hospitalization of unstable angina, or non-elective coronary revascularization;
- The number of total events: CV death, non-fatal MI, non-fatal stroke, hospitalization of unstable angina, or all coronary revascularization;
- The number of total events: CHD death, non-fatal MI, non-fatal stroke, hospitalization of unstable angina, or non-elective coronary revascularization;
- The number of total events: CHD death, non-fatal MI, non-fatal stroke, hospitalization of unstable angina, or all coronary revascularization;
- The number of total events: CV death, non-fatal MI, non-fatal stroke, hospitalization of unstable angina, MALE or non-elective coronary revascularization;
- The number of total events: CV death, non-fatal MI, non-fatal stroke, hospitalization of unstable angina, MALE or all coronary revascularization;

- The number of total events: CHD death, non-fatal MI, non-fatal stroke, hospitalization of unstable angina, MALE or non-elective coronary revascularization;
- The number of total events: CHD death, non-fatal MI, non-fatal stroke, hospitalization of unstable angina, MALE or all coronary revascularization;
- The number of total events: CV death, non-fatal MI, non-fatal stroke, hospitalization of unstable angina, MALE, other atherosclerotic events (AAA, TIA, carotid revascularization) or non-elective coronary revascularization;
- The number of total events: CV death, non-fatal MI, non-fatal stroke, hospitalization of unstable angina, MALE, other atherosclerotic events (AAA, TIA, carotid revascularization) or all coronary revascularization;
- The number of total events: CHD death, non-fatal MI, non-fatal stroke, hospitalization of unstable angina, MALE, other atherosclerotic events (AAA, TIA, carotid revascularization) or non-elective coronary revascularization;
- The number of total events: CHD death, non-fatal MI, non-fatal stroke, hospitalization of unstable angina, MALE, other atherosclerotic events (AAA, TIA, carotid revascularization) or all coronary revascularization; and
- The number of total CV events.

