6 CHANGES FROM PROTOCOL-SPECIFIED STATISTICAL ANALYSES

There have been three changes from the protocol v6.0.

The first change is the addition of time points to the exploratory endpoint, Day 84 and Day 180, to evaluate trough levels of obicetrapib from Baseline.

The second change relates to the effect of obicetrapib on cardiovascular events. Additional exploratory endpoints were added:

- The time from Randomization until the first confirmed occurrence of a composite of CV death, non-fatal MI, or non-fatal stroke, or coronary revascularization
- The time from Randomization until the first confirmed occurrence of a composite of CHD death, non-fatal MI, or non-fatal stroke, or non-elective coronary revascularization
- The time from Randomization until the first confirmed occurrence of a composite of CHD death, non-fatal MI, or non-fatal stroke, or coronary revascularization
- The time from Randomization until the first confirmed occurrence of a composite of CHD death, non-fatal MI, or non-fatal stroke
- MALE events
- Number of total CV events.

The third change is the inclusion of subgroup analysis.

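### The SAP's exploratory CHD-death endpoints count a survived stroke but, on the plain reading, not a fatal one

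*SAP*

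**What the plan says.** The protocol's own composites (Protocol 7) pair CV death with non-fatal MI and non-fatal stroke. Fatal stroke is covered there because "CV death is defined as death resulting from an acute MI, sudden cardiac death, death due to HF, death due to stroke" and further causes.

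The SAP adds a parallel family built on CHD death. SAP 2.1.3 introduces it with "Coronary heart disease (CHD) death, non-fatal myocardial infarction (MI), non-fatal stroke, or non-elective coronary revascularization". SAP 2.3.3 carries it through time-to-first endpoints, from the "first confirmed occurrence of a composite of CHD death, non-fatal MI, or non-fatal stroke" to the broadest version, "CHD death, non-fatal MI, non-fatal stroke, hospitalization of unstable angina, MALE, other atherosclerotic events (AAA, TIA, carotid revascularization), or coronary revascularization". It does the same for total-event counts, such as "The number of total events: CHD death, non-fatal MI, non-fatal stroke" and "The number of total events: CHD death, non-fatal MI, non-fatal stroke, or all coronary revascularization". SAP 6 repeats the three-component form among the changes from the protocol ("composite of CHD death, non-fatal MI, or non-fatal stroke"). In each case the only stroke component is non-fatal stroke.

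SAP 3.4.3 censors participants in whom the event did not occur, with time running to early termination or end of study. It gives no separate rule for deaths that are not components.

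**The concern.** Pairing a death component with non-fatal stroke works only if the death component takes in stroke deaths. CV death does. CHD death, expanded in the SAP only as coronary heart disease, does not on its ordinary meaning. Changing the death term without changing the stroke term leaves fatal stroke outside both components.

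The worse outcome then scores as the better one. A shift from survived to fatal strokes in one arm would reduce that arm's CHD events. Each CHD result will also be read beside its CV-death counterpart, and part of any difference between them would come from this omission and not from coronary disease.

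**Working it through.** **Count of affected endpoints (SAP 2.3.3).** There are 46 cardiovascular endpoint bullets. Those using CHD death are 10 time-to-first and 9 total-event: 10 + 9 = 19. The three-component time-to-first endpoint is listed twice, so 19 − 1 = 18 are distinct. None of the 19 lists fatal stroke, stroke of any outcome, or CV death. Each of the 18 has a CV-death counterpart with otherwise the same components.

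**Where a stroke death falls.** Protocol 7.2.1 gives it its own category ("Death due to stroke refers to death after a stroke", as a direct consequence or a complication). Appendix F does the same. Acute MI and sudden cardiac death are separate categories. One exception matters: a CV death within 30 days of an MI, including through stroke, is classed as death due to acute MI. That would be a CHD death on a coronary reading.

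**Scoring four courses**, taking CHD death as coronary death and a stroke that causes death as not non-fatal:

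| Course | CV-death composite (time to first) | CHD-death composite (time to first) | Added to CHD total count |
|---|---|---|---|
| Stroke Day 200, alive at end of study | Event | Event | 1 |
| Stroke Day 200, dies of it Day 201, no earlier component event | Event | Censored | 0 |
| Non-fatal MI Day 100, fatal stroke Day 200 | Event Day 100 | Event Day 100 | 1 (the MI only) |
| MI Day 190, dies through stroke Day 200 | Event | Event (death classed as acute MI) | At least 1 |

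The second row is the problem in the time-to-first analyses. The second and third rows show it in the total counts.

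**Direction, with assumed case fatality.** Suppose stroke incidence is equal in the arms, and 30% of strokes are fatal on active treatment and 10% on placebo. The non-fatal stroke component alone then has ratio (1 − 0.30)/(1 − 0.10) = 0.70/0.90 = 0.78, in favour of the arm with more stroke deaths. The other components would dilute this.

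**Size.** The plan gives no figure to reproduce: no stroke rate, stroke share of events, or case fatality. As an assumed range only, take 2400 participants followed for 365 + 35 = 400 days and a stroke rate of 0.5% to 2% per year:

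- Strokes: 2400 × 400/365 × 0.005 = 13.2, up to 2400 × 400/365 × 0.02 = 52.6.
- Fatal strokes at 10% to 30% case fatality: 13.2 × 0.10 = 1.3, up to 52.6 × 0.30 = 15.8.

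That is about 1 to 16 fatal strokes in both arms together. It is a ceiling on those lost under these assumptions, because the third course still counts in the time-to-first analyses and the fourth counts in both.

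**The case against.** The strongest reply is that the scoring rests on undefined terms. CHD death is defined nowhere, and CEC procedures sit in a charter outside these documents that might define it to include stroke death. Non-fatal has no survival window either, so a stroke followed some days later by death could be scored either way. This stands as a limit on certainty: the second row of the table is the plain reading, not a rule the documents spell out. It does not remove the point, because nothing in the protocol or SAP extends CHD death to stroke, and the missing definitions are part of what needs repair.

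The second reply is that little depends on these endpoints. They are exploratory, with no multiplicity adjustment (SAP 3.1.6), and stroke deaths remain visible in the CV-death counterparts, in CV death, in all-cause death, and in the summaries of adverse events leading to death. This also stands. A reader might infer that the trial could miss an excess of fatal strokes; the documents do not support that.

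Third, censoring at a non-component death is not peculiar to stroke. SAP 3.4.3 treats every such death this way, including non-CV deaths in the CV-death composites. That is correct, so informative censoring is not a separate charge here. What is specific is that the survived form of the same event is a component and the fatal form is not.

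**Conclusion.** The point holds for the 19 CHD-death endpoints in SAP 2.3.3 (18 distinct), on the coronary reading of CHD death. A first component-type event that is a fatal stroke, and is not classed as death due to acute MI, is censored in the time-to-first analyses. The stroke death adds nothing to the total counts, while a survived stroke is an event.

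A reader might go further and infer that every fatal stroke is lost from every CHD endpoint. That is too strong: in the time-to-first analyses an earlier component event still counts, and stroke deaths within 30 days of an MI are classed with MI. Nor can a percentage loss be stated, since the documents supply no rates; the counts above are assumptions. No primary or secondary result is touched. The matter is modest in weight but worth correcting, because the error runs in a perverse direction and is cheap to remove.

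**What to change.** Amend SAP 2.1.3, 2.3.3 and 6 before unblinding:

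1. In every CHD-death composite and CHD total-event endpoint, replace non-fatal stroke with *fatal or non-fatal stroke*.
2. Define CHD death by stating which Protocol 7.2.1 cause-of-death categories it includes.
3. State the boundary between fatal and non-fatal stroke, so that a stroke and the death it causes are counted once.

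If leaving out fatal stroke is intended, the SAP should say so and state how stroke deaths and other non-CHD deaths are handled in these analyses.

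The cost is mainly wording. The CEC already adjudicates all deaths, and CHD death cannot be scored without a cause. The small downside is that stroke must be recorded as a cause of death, whereas Appendix F leaves subclassification of CV death optional. Whether the CEC already records it cannot be seen from these documents.
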